## **1. OBJECTIVES**

### **1.1 Primary Objective**

- 1.1.1 To determine the objective response rate (ORR) of advanced, progressive, well-differentiated nonfunctional NET of the lung, pancreas or gastrointestinal (GI) tract treated with nivolumab plus ipilimumab.

### **1.2 Secondary Objectives**

- 1.2.1 To assess safety and tolerability of nivolumab plus ipilimumab by quantification of treatment dose interruptions and characterization of toxicities of the combination of nivolumab and ipilimumab in subjects with advanced well-differentiated nonfunctional NET of the lung, pancreas or GI tract.
- 1.2.2 To assess efficacy via progression free survival (PFS) at 6 months, 12 and 24 months of the combination of nivolumab and ipilimumab in subjects with advanced well-differentiated nonfunctional NET of the lung, pancreas or GI tract.
- 1.2.3 To further assess efficacy via median PFS, disease control rate (DCR), duration of response (DOR) and overall survival (OS) of the combination of nivolumab and ipilimumab in subjects with advanced well-differentiated nonfunctional NET of the lung, pancreas or GI tract.

### **1.3 Exploratory Objectives**

- 1.3.1 To assess immunogenicity, response characteristics, and predictors of toxicity of nivolumab in combination with ipilimumab by evaluating peripheral blood mononuclear cells (PBMCs), sera, plasma and tumor samples collected in treated subjects.

### **1.4 Study Design**

The study population will include subjects with advanced thoracic, GI and pancreatic neuroendocrine tumors. We propose an open-label, single arm phase 2 study of nivolumab in combination with ipilimumab. All subjects will be assigned to receive Nivolumab: 240 mg IV q2 weeks plus ipilimumab: 1 mg/kg IV q6 weeks.

## STUDY SCHEMA

**Advanced or metastatic non-functional, well differentiated thoracic, GI or pancreatic NET  
No prior PD-1/PD-L1/CTLA-4 therapy  
ECOG PS 0-1**

**Nivo 240 mg Q2wks + Ipi 1mg/kg Q6wks  
Enrollment by tumor site of origin**

**Treat until disease progression or unacceptable toxicity**

## 2. BACKGROUND

### 2.1 Neuroendocrine tumors (NETs)

Well-differentiated neuroendocrine tumors (NETs), often referred to as carcinoid tumors, are a heterogeneous group of malignancies originating in neuroendocrine cells throughout the body(1). They are anatomically, functionally and histopathologically distinguished in an effort to optimize their care. Based on population-based registries, about 51% of NETs originate in the gastrointestinal (GI) tract, 27% in the lungs and 6% in the pancreas(1). Functional NETs cause carcinoid syndrome, due to hormonal hypersecretion. In the ~25% of patients with functional NETs, symptoms are often managed by a somatostatin analogue, such as octreotide or lanreotide. These medications have also been shown to delay tumor progression in advanced GI NETs (2, 3); as such they are commonly used in this disease setting, although are not FDA-approved for this indication. Nonfunctional NET (~70%) patients often develop symptoms due to tumor growth, such as intestinal obstruction, pain and bleeding for GI NETs, and asthma, chronic obstructive pulmonary disease and pneumonia for lung NETs (4-7). At presentation, 5-44% of patients with GI NET and 28% of patients with lung NET have advanced disease, and progression is typically associated with poor outcomes. Advanced or metastatic NETs, irrespective of function or histopathologic grade, are incurable with current treatment regimens.

Recently, everolimus has been FDA approved for the treatment of progressive, well-differentiated nonfunctional pancreatic, bronchopulmonary and GI NETs [Everolimus FDA]. The RADIANT trials were integral to this treatment approval. RADIANT-1 was a Phase II trial that evaluated Everolimus in patients with metastatic pancreatic NETs with

disease progression after cytotoxic chemotherapy; results revealed median progression free survival (mPFS) of 9.7-16.7 months as stratified by prior octreotide therapy (8). RADIANT-2 was a Phase III trial that evaluated Everolimus in advanced, non-functional NETs of the lung or GI tract which revealed mPFS of 11 months as compared to 3.9 months in the placebo group (9). RADIANT-3 was a Phase III trial that evaluated Everolimus in advanced, low-grade or intermediate grade pancreatic NET that revealed an 11 month mPFS compared to 4.6 months with placebo (10). RADIANT-4 was a Phase III trial that evaluated Everolimus in advanced, non-functional NETs of the lung or GI NET that reported an 11 month mPFS compared to a 3.9 month mPFS with placebo (11).

Thoracic NETs are histopathologically subdivided into typical carcinoid (TC) and atypical carcinoid (AC) tumors(12) and comprise 2.2% of lung cancers diagnosed in the US annually (7, 13). AC is the more common and more aggressive phenotype. There is a paucity of data regarding systemic therapy for advanced thoracic NET disease outside of the recently published RADIANT-4, and is based mainly on small retrospective series and subgroup analyses of predominant gastrointestinal neuroendocrine tumor clinical trials, leading to a lack of definitive data for systemic regimen recommendations outside of everolimus placebo (11). Forde et al., reported on a systematic analysis of thoracic NET patients at Johns Hopkins. The response rate to platinum plus etoposide chemotherapy for both advanced TC and AC was 23.5% (14).

GI NETs arise in the stomach, intestine, appendix, colon or rectum with an incidence of approximately 8000 cases annually in the US(15). The 5-yr OS rates in advanced well and moderately-differentiated neuroendocrine tumors range from 14-54% by anatomic location. The PROMID study showed an improvement in time to tumor progression in advanced midgut NET patients treated with octreotide LAR (long acting release (2) The recent advances of use of Everolimus in the RADIANT series have shown improved outcomes in some endpoints, leading to FDA approval, but does not frequently cause a response with tumor shrinkage (9, 11).

Pancreatic NETs account for <4% of all pancreatic cancers; about half of them are functional, benign tumors. Non-functional pancreatic NETs are more likely to be malignant. The CLARINET trial showing significant improvement in PFS in pancreatic NET patients treated with lanreotide vs. placebo (3). Based on the results of RADIANT-1 and RADIANT-3, everolimus is FDA-approved and commonly used in advanced pancreatic NET (8, 10). Sunitinib can also be used in this patient population (16).

## 2.2 **PD-L1 Expression in NETs**

PD-L1 staining in gastro-entero-pancreatic (GEP) NETs has been reported in by Kim et al.; of 24 foregut GEP-NETs, PD-L1 staining was observed in 21.9%, was significantly associated with high-grade classification and predicted for poorer survival (17). In a series of 66 GEP NETs, Pinato et al., reported a lower rate of PD-L1 staining ( 9%) but high PD-L2 (50%) (18). Fan et al., reported high PD-L1 (59%) and PD-1 (51%) staining in pulmonary NET tissue compared to cancer-adjacent tissue from 80 cases (19). Multivariate analyses revealed that expression of PD-L1 and PD-1 were negatively associated with survival time.

## 2.3 Nivolumab and Ipilimumab

Immunotherapeutic approaches have demonstrated clinical efficacy in several cancer types, including melanoma, non-small cell lung cancer (NSCLC), renal cell carcinoma (RCC), head and neck cancer, bladder and hormone-refractory prostate cancer (20). Tumors modulate and evade the host immune response through a number of mechanisms, including down regulation of tumor-specific antigen expression and presentation, secretion of anti-inflammatory cytokines, and upregulation of inhibitory ligands. T cell checkpoint regulators such as CTLA-4 and programmed death-1 (PD-1, CD279) are cell surface molecules that, when engaged by their cognate ligands, induce signaling cascades down-regulating T cell activation and proliferation. PD-1 and CTLA-4 are both co-inhibitory molecules, but evidence suggests that they use distinct mechanisms to limit T cell activation.

CTLA-4 mediated signals are inhibitory to T cell-dependent immune responses (21). Ipilimumab is a fully human monoclonal IgG1κ that binds to the CTLA-4 antigen expressed on a subset of T cells from human and nonhuman primates. The proposed mechanism of action for ipilimumab is interference of the interaction of CTLA-4 with B7 molecules on APCs, with subsequent blockade of the inhibitory modulation of T-cell activation promoted by the CTLA 4/B7 interaction. Ipilimumab was approved by FDA for the treatment of patients with BRAF V600 wild-type, unresectable or metastatic melanoma.

Nivolumab (BMS-936558) is a fully human, IgG4 (kappa) isotype mAb that binds PD-1 on activated immune cells and disrupts engagement of the receptor with its ligands PD-L1 (B7-H1/CD274) and PD-L2 (B7-DC/CD273), thereby abrogating inhibitory signals and augmenting the host antitumor response. In clinical trials, nivolumab has demonstrated activity in several tumor types, including melanoma, renal cell cancer (RCC), and NSCLC leading to widespread FDA-approval (22).

### 2.3.1 Combination treatment with nivolumab and ipilimumab

Multiple studies in several cancer types have evaluated the safety and efficacy of combination on nivolumab and ipilimumab. In both melanoma and non-small cell lung cancer (NSCLC) these data show that the combination of nivolumab and ipilimumab is well tolerated and associated with promising durable responses. In melanoma, CA209004 (MDC1106-04) was a phase Ib study in subjects with previously treated advanced melanoma. CA209069 and CA209067, a phase 2 and phase 3 studies, respectively, in treatment-naïve subjects with advanced melanoma (23, 24). This final study reported significantly improved PFS and ORR with the combination of nivolumab and ipilimumab versus ipilimumab alone in previously untreated melanoma. The mPFS was 6.9 mos in the nivolumab group compared with 11.5 mos in the nivolumab-plus-ipilimumab group.

CA209012, was an open-label, phase 1, multicohort study in treatment-naïve subjects with advanced NSCLC. In this study, multiple dosing regimens were explored. The final report included 78 patients randomly assigned to: 1) nivolumab 3mg/kg every 2 weeks plus ipilimumab 1mg/kg every 6 weeks or 2) nivolumab 3mg/kg every 2 weeks plus ipilimumab 1mg/kg every 12 weeks (25).

Grade 3-4 treatment related AEs were reported in 37% and 33% of subjects respectively, most commonly increased lipase, pneumonitis and adrenal insufficiency, colitis. Confirmed responses were reported in 47% in the ipilimumab 6 week cohort and 38% of the ipilimumab 12-week cohort.

## 2.4 Study Rationale

Subjects with progressive, non-functional advanced or metastatic thoracic, GI or pancreatic well-differentiated NETs are have few treatment options. The only FDA approved treatment regimen offers little response potential. In currently unpublished data with inhibitory immune checkpoint agents, patients with NET have shown promising clinical benefit. This therapy offers a novel approach to potentially provide long term benefit, but must be further explored.

The safety profile of nivolumab plus ipilimumab is characterized by immune-related toxicities, such as diarrhea, rash, pneumonitis, liver toxicity, and endocrinopathies (Nivolumab, Ipilimumab Investigator's Brochures). The frequencies and intensities of these events in the combination are variable and depend on the specific doses and schedule used. In the dosing schedules selected, these events were mostly low grade and manageable with the use of corticosteroids. Nivolumab and ipilimumab combination therapy has shown improved efficacy over either agent alone in melanoma.

### 2.4.1 Rationale for Single Arm Design

This study will use a single arm open-label design. The objective of this study is to evaluate the objective response rate of combination nivolumab and ipilimumab in advanced, well-differentiated neuroendocrine tumors. Durability of response, and PFS will also be described.

Response rates to everolimus, the only FDA approved regimen for this patient population, are well documented in the RADIANT trials. The ORR to everolimus in advanced, progressive low-intermediate grade pancreatic NET was 5% (vs. 2% with placebo), and 2% in advanced, progressive well-differentiated nonfunctional lung and GI NET (vs. 1% with placebo) (10, 11).

### 2.4.2 Rationale for Exploratory Correlative Studies

Exploratory correlative studies will be performed to evaluate immune system activation and for potential biomarker identification. The specific studies proposed include: 1) assessment of immune cell composition by IHC, gene expression profiling and cytokine production within the TME; 2) whole genome or exome sequencing to assess mutational load and potentially identify predictors of response or resistance; 3) plasma-based markers to correlate with response.

Paired pre-treatment and on treatment core biopsies will be mandatory for patients on the part 2 of this study and optional for patients on part 1. Biopsies at time of progression will be optional. Blood samples will be collected prior to treatment and during treatment as described in the study calendar.

#### 2.4.2.1 Tissue studies

##### Tumor Microenvironment (TME) Analysis

Quantification, qualification and distribution of immune cell infiltrates may correlate to response and clinical outcome. The densities and distribution of effector T cells (Teff) including CD8, CD45RO, CXCR3 and CD69+ cells; expression of immune suppressive signals including PD-1, PD-L1, PD-L2, LAG3, TIM3, and IDO1; immune activation signals including CD137(4-1BB), 4-1BBL, OX40, OX40L, CD40, and CD40L on T cells and macrophages, and the expression of T helper cell differentiation markers including Tbet (for Th1), GATA3 (for Th2), ROR  $\gamma$  T (for Th17), and Foxp3 (for Treg) have been found to be clinically relevant (Lutz et al. 2014). The balance between Teff and regulatory T cell (Treg) function is an area of active study as well.

##### Quantitative Gene Expression

Evaluation of the balance between various immune cell types (Th1 vs. Th2; M1 vs M2; Teff vs. Treg) is imperative to understand the qualitative and quantitative effect of dual checkpoint blockade. The expression signatures of certain genes already found to be potentially linked to clinical benefit in other tumor types should be compared to the gene expression signatures found to correlate with response in NET patients. Intra-tumoral cytokine array analysis will also further describe the immunogenic tumor microenvironment.

##### Intratumoral Antigen Specific T cell Response

Tumor antigen-specific T cells that traffic into the tumor are the most relevant T cells to study when evaluating antitumor immune responses. Both peripheral (peripheral blood lymphocytes, (PBL)) and tumor-infiltrating lymphocytes (TIL) T-cell receptor (TCR) repertoires will identify T cells that expand following treatment. Peripheral and TIL TCR repertoire comparisons will be used to identify any T cell clones that are induced or expanded in PBL by combination treatment and also enriched in TIL. This data will be used to determine if T cells in PBL and TIL undergo clonal expansion following treatment, and if so, whether the T cell clones traffic to the carcinoid TME.

##### Whole exome sequencing to detect somatic alterations

Next generation sequencing may be performed to identify of genomic correlates of response and resistance. Nonsynonymous missense mutations identified will be used to predict mutant peptides and generate a neoantigen signature for each tumor using a computational pipeline we have developed. A separate targeted capture and sequencing analysis of the TCR will be performed to assess T cell clonality

#### 2.4.2.2 Serum and Plasma Studies:

Various factors that may impact the immunomodulatory properties and efficacy of nivolumab and ipilimumab will be investigated in peripheral blood specimens

taken from all subjects prior to or during treatment. Data from these investigations will be evaluated for associations with response, survival, and/or safety (adverse event) data. Plasma samples will be obtained at baseline, on treatment and at progression.

#### Circulating Tumor DNA (ctDNA)

Non-invasive genomic approaches to determine somatic mutations that detect residual disease are being developed at our institution. Cancer-specific genomic alterations in circulating cell free DNA (ctDNA) are being evaluated for potential to assess ability to predict disease response or progression prior to conventional CT imaging. Peripheral tumor-specific mutations found following disease progression can be compared to the patient's genomic tumor profile to evaluate for potential matching resistance mutations.

### **3. PATIENT SELECTION**

#### **3.1 Eligibility Criteria**

- 3.1.1 Subjects with histologically confirmed advanced, progressive, well-differentiated nonfunctional NET of the pancreas, lung or gastrointestinal (GI) tract per the 8th International Association for the Study of Lung Cancer classification (IASLC) or the American Joint Committee on Cancer (AJCC) Staging Handbook, 7th edition. Progression must be documented over the prior 12 months.
- 3.1.2 Measurable disease by CT or MRI per RECIST 1.1 criteria (Appendix 3); radiographic tumor assessment performed within 28 days before treatment. Target lesions may be located in a previously irradiated field if there is documented (radiographic) disease progression in that site after the completion of radiation therapy.
- 3.1.3 Prior therapy, including everolimus, octreotide, surgery, chemoradiation, is all permitted after being properly noted. This prior therapy must have been completed at least 28 days prior to study enrollment.
- 3.1.4 Patients with lung NETs must have progressed after at least 1 line of therapy. Patients with GI NETs must have had at least 2 lines of prior therapy.
- 3.1.5 Subjects are to have tumor tissue sample available at central lab for PD -L1 IHC testing during the screening period. Subjects can initiate therapy before the result of IHC testing.
- 3.1.6 (Stage 2 only) Subjects must be willing to undergo 2 sets of core needle biopsies (pre-treatment and at 6-8 weeks on therapy) if there are lesions amenable to biopsy. Subjects without a lesion amendable to biopsy will still be permitted to enroll provided they have an archival tumor sample for PD-L1 IHC testing. An optional core biopsy will be requested at progression.

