## 3.2 Exclusion Criteria

3.2.1 Subjects with poorly differentiated or small cell carcinoma histology

3.2.2 Subjects with disease that is amenable to surgical resection.

3.2.3 Subjects with history of or active symptoms of carcinoid or hormonal syndromes are permitted if symptoms are controlled with a somatostatin analog.

3.2.4 Hepatic intra-arterial embolization or peptide receptor radionuclide therapy (PRRT) within 4-8 weeks; cryoablation, radiofrequency ablation or trans-arterial chemoembolization of hepatic metastases within  $\leq$  4 weeks of study enrollment

3.2.5 Subjects with symptomatic untreated CNS metastases are excluded.

3.2.5.1 Subjects are eligible if CNS metastases are asymptomatic or adequately treated and subjects are neurologically returned to baseline (except for residual signs or symptoms related to the CNS treatment) for at least 2 weeks prior to first treatment.

3.2.5.2 In addition, subjects must be either off corticosteroids, or on a stable or decreasing dose of  $\leq$ 10 mg daily prednisone (or equivalent) for at least 2 weeks prior to first treatment.

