### 11.1.2 Disease Parameters

**Measurable disease.** Measurable lesions are defined as those that can be accurately measured in at least one dimension (longest diameter to be recorded) as  $\geq 20$  mm ( $\geq 2$  cm) by chest x-ray or as  $\geq 10$  mm ( $\geq 1$  cm) with CT scan, MRI, or calipers by clinical exam. All tumor measurements must be recorded in millimeters (or decimal fractions of centimeters). Tumor lesions that are situated in a previously irradiated area may only be considered measurable if they are growing on pre-treatment imaging.

**Malignant lymph nodes.** To be considered pathologically enlarged and measurable, a lymph node must be  $\geq 15$  mm ( $\geq 1.5$  cm) in short axis when assessed by CT scan (CT scan slice thickness recommended to be no greater than 5 mm [0.5 cm]). At baseline and in follow-up, only the short axis will be measured and followed.

**Non-measurable disease.** All other lesions (or sites of disease), including small lesions (longest diameter  $<10$  mm [ $<1$  cm] or pathological lymph nodes with  $\geq 10$  to  $<15$  mm [ $\geq 1$  to  $<1.5$  cm] short axis), are considered non-measurable disease. Bone lesions, leptomeningeal disease, ascites, pleural/pericardial effusions, lymphangitis cutis/pulmonitis, inflammatory breast disease, and abdominal masses (not followed by CT or MRI), are considered as non-measurable.

**Target lesions.** All measurable lesions up to a maximum of 2 lesions per organ and 5 lesions in total, representative of all involved organs, should be identified as **target lesions** and recorded and measured at baseline. Target lesions should be selected on the basis of their size (lesions with the longest diameter), be representative of all involved organs, but in addition should be those that lend themselves to reproducible repeated measurements. It may be the case that, on occasion, the largest lesion does not lend itself to reproducible measurement in which circumstance the next largest lesion which can be measured reproducibly should be selected. A sum of the diameters (longest for non-nodal lesions, short axis for nodal lesions) for all target lesions will be calculated and reported as the baseline sum diameters. If lymph nodes are to be included in the sum, then only the short axis is added into the sum. The baseline sum diameters will be used as reference to further characterize any objective tumor regression in the measurable dimension of the disease.

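### Entry does not require progression after the most recent therapy, and only irradiated target lesions must have progressed since treatment, so late shrinkage from prior therapy could count in the primary ORR

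*Combined protocol and SAP*

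**What the plan says.** All references are to the combined protocol and SAP.

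- **Progression at entry (3.1.1).** Disease must be advanced and progressive, and "Progression must be documented over the prior 12 months". The primary objective (1.1.1) also describes the disease as progressive. Neither place relates the progression to the last treatment.
- **Washouts (3.1.3, 3.2.4).** For earlier treatment in general, "This prior therapy must have been completed at least 28 days prior to study enrollment". The exclusion for liver-directed and radionuclide treatment reads "Hepatic intra-arterial embolization or peptide receptor radionuclide therapy (PRRT) within 4-8 weeks", with a separate four-week window for ablation and chemoembolization. These are time limits only.
- **Prior lines (3.1.4).** "Patients with lung NETs must have progressed after at least 1 line of therapy", and "Patients with GI NETs must have had at least 2 lines of prior therapy". Nothing is said about pancreatic NETs.
- **Target lesions (3.1.2, 11.1.2).** "Target lesions may be located in a previously irradiated field if there is documented (radiographic) disease progression in that site" once radiotherapy is complete. Section 11.1.2 repeats the idea: lesions in an irradiated area "may only be considered measurable if they are growing on pre-treatment imaging".
- **Response (11.1.4.1, 12.3.1).** PR is a fall of at least 30% from the baseline sum of diameters, confirmed at least 4 weeks later. Best overall response is cut off by progression, palliative local therapy or a new anticancer treatment. No rule deals with effects of earlier treatment.

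**The concern.** With no control arm, tumour shrinkage caused by the previous treatment looks the same as shrinkage caused by nivolumab plus ipilimumab. Suppose a subject progressed ten months ago, was then embolized or given chemotherapy, and cleared the washout. Nothing in 3.1 or 3.2 expressly requires new progression since that treatment. If the lesions go on shrinking after the baseline scan, the subject can become a confirmed PR.

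The plan already accepts the principle for irradiated lesions but stops there. Confirmation does not separate the two causes, because a continuing earlier effect would also confirm. Section 11.1.7 plans no independent radiology review.

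Any such error favours the regimen, and the counts that decide the trial in 12.2 are small: 2 responders among 20 to continue, and 5 among 56 to declare activity.

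**Working it through.** **Is the gap in the text?**

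| Subject | What ties progression to the latest therapy? |
|---|---|
| Lung, exactly one prior line | 3.1.4: covered |
| Lung, two or more lines | Progression after an earlier line would satisfy 3.1.4 |
| GI | Two lines must have been given; progression after them is not mentioned |
| Pancreatic | No prior-line rule |

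| Target lesion treated by | Must it have progressed since? |
|---|---|
| External radiation | Yes (3.1.2, 11.1.2) |
| PRRT | Unclear whether this counts as irradiation |
| Embolization, ablation | No rule |

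**What could be miscounted?** Only shrinkage after the baseline scan. That scan may be up to 28 days before first dose (3.1.2), while the 28-day washout runs to enrollment (3.1.3). If enrollment and first dose are close together, the scan may fall soon after the earlier treatment ended, so the washout does not guarantee a scan taken late in it.

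**Reproducing the plan's design (12.2).** Inputs: 20 subjects in stage 1, stop at 1 or fewer responders; 56 in total, reject the regimen at 4 or fewer; null rate 0.05, alternative 0.15.

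- Early stop at p = 0.05: 0.95^20 + 20 × 0.05 × 0.95^19 = 0.358 + 0.377 = 0.736.
- Expected N: 20 + (1 − 0.7358) × 36 = 29.51.
- P(declare active) = sum over x ≥ 2 of Bin(x; 20, p) × P[Bin(36, p) ≥ 5 − x], which is 0.0967 at p = 0.05 and 0.801 at p = 0.15.

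All agree with the stated 0.736, 29.51, 0.097 and 0.199 (1 − 0.801).

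**Effect of one carry-over responder.** Fix k1 such responders in stage 1 and k2 in stage 2, and let everyone else respond at rate p:

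P = sum over x with x + k1 ≥ 2 of Bin(x; 20 − k1, p) × P[Bin(36 − k2, p) ≥ 5 − x − k1 − k2].

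| Carry-over responders | p = 0.05 | p = 0.02 |
|---|---|---|
| None | 0.097 | 0.003 |
| One in stage 1 | 0.256 | 0.020 |
| One in stage 2 | 0.165 | 0.012 |

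The 5% column uses the plan's null. The 2% column uses the upper of the two placebo response rates in 2.4.1 (1% and 2%).

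**Passing the interim rule at p = 0.05.** Without carry-over: 1 − 0.736 = 0.264. With one carry-over responder in stage 1, one more response among the other 19 is enough: 1 − 0.95^19 = 0.623. A wrong pass enrols 36 more subjects.

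**Under the criterion in 12.4.1.** This asks for a 95% Clopper-Pearson lower bound above 15%. With 14 of 56 the bound is 14.4%; with 15 of 56 it is 15.8%. So 15 responders are needed, and one miscounted responder hardly affects the final decision. The interim rule is unchanged.

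**The case against.** The strongest reply starts with the word progressive in 3.1.1. It describes current disease, and the 12-month sentence can be read as saying only how that status is documented. A reader might infer that a subject whose tumours are still shrinking plainly qualifies. The documents do not support that: an investigator could properly refuse such a subject. What stands is that the wording is ambiguous, and that it does not exclude someone treated since the documented progression.

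There are real safeguards: the washouts, a fresh baseline scan, a further 30% fall with confirmation, and full cover for the single-line lung subject. They reduce the number of possible cases without removing them.

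A reader might also infer a large inflation of the error rate. If a share f of subjects carries over with response chance c, the null rate becomes 0.05 + 0.95fc. Taking f and c at 5% each gives 0.052 and false success of 0.111; f = 30% with c = 20% gives 0.107 and 0.557. Those inputs are assumptions; the documents give neither. Section 2.4.1 reports everolimus response rates of 2% and 5%, and late shrinkage after washout should be rarer than response overall. Section 2.1 does give 23.5% for platinum plus etoposide in thoracic disease, so a very low rate cannot be assumed for every prior treatment. No estimate of the bias is justified either way.

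Finally, the window may be a deliberate accrual choice, and a tighter rule narrows entry. That is fair, and is why a lighter alternative is offered below.

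**Conclusion.** The point holds as a gap in wording with a possible bias in favour of the regimen; it does not show that the ORR will be materially inflated. Progression is not expressly tied to the most recent therapy, and the lesion-level safeguard reaches irradiated sites only.

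The size is a conditional sensitivity. It assumes that one carry-over responder occurs, that the 12.2 rule decides, and that all others respond at 5%. False success then goes from 9.7% to 25.6% or 16.5%, and the chance of passing the interim rule from 26% to 62% if that responder is in stage 1. At a background rate of 2%, false success stays at or below about 2%. If 12.4.1 governs, the consequence is confined almost entirely to the interim decision. The conflict between 12.2 and 12.4.1 is a separate matter that must be reconciled. This is a cheap improvement worth making.

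**What to change.** 1. **Target lesions (3.1.2 and 11.1.2).** Extend the existing irradiated-lesion rule: a lesion previously treated by embolization, ablation or PRRT may be a target lesion only if it has progressed since that treatment. This also settles the PRRT ambiguity. It costs one clause in each section.
2. **Eligibility (3.1.1).** State that the documented progression must be on or after the most recent anticancer therapy. It costs one sentence. The downside is that some subjects, such as those who stopped their last therapy for toxicity without progressing, would have to wait or be excluded.
3. **Lighter alternative to item 2**, if it would hinder accrual or subjects are already enrolled: record for each subject whether progression has occurred since the last therapy, and add to 12.4.1 an ORR sensitivity analysis that counts responders without such progression as non-responders and keeps them in the denominator. It costs one data field and one table.

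None of these alters the sample size, the primary endpoint, the treatment or the washout periods.
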